### **5.5.3. Prohibited Medications During the Study**

- Any investigational agent within 30 days or 5 therapeutic half-lives of that agent, whichever is longer, before Visit 1 and throughout the study.
- Any cannabinoid, including recreational marijuana, medicinal marijuana or other prescription cannabinoids are prohibited from Screening throughout the study.

## **6. DISCONTINUATION OF STUDY TREATMENT, SUBJECT WITHDRAWAL, AND EARLY TERMINATION**

### **6.1. Discontinuation of Study Treatment and Subject Withdrawal**

Subjects are free to withdraw from participation in the study at any time upon request.

A subject will not receive any further study product if any of the following events occur:

- Subject lost to follow-up
- Withdrawal of consent for study participation
- Subject decision to discontinue treatment
- Pregnancy
- Any serious or life-threatening AE probably or definitely-related to lenabasum
- Any AE, which in the opinion of investigator, can jeopardize the safety of an individual subject
- Subjects recognized as being treated despite being wrongly randomized (i.e., not meeting all eligibility criteria)
- Other event(s) which in the opinion of the site investigator or Medical Monitor contraindicates further dosing such as, but not limited to, repeated failure to meet protocol requirements, significant concurrent illnesses or disease complications

Subjects withdrawn for the above reasons, except lost to follow-up or withdrawn consent, will be asked to return to Visit 4, Visit 6, Visit 8 (if they have not already had Visit 4, 6, and 8), and Visit 10; Weeks 16, 28, 40 and 52, respectively. These subjects will not be required to but may undergo optional blood sampling, skin photography, or skin biopsies at the remaining visits if they had opted in previously.

Subjects who are discontinued permanently from drug therapy due to an AE related to study product will be followed until resolution or stabilization of the event. Subjects who are withdrawn due to pregnancy, or partners of subjects who become pregnant, will require additional follow-up as outlined in Pregnancies, [Section 8.2.7.8](#).

Subjects who withdraw consent will be asked to complete the early termination (ET) visit; however, completion of the visit will not be mandated.

A subject will be considered lost to follow-up if he/she does not respond to the following:

- Three attempts at contacting the subjects (including phone calls, emails, or texts and a certified letter) from a member of the research staff over a period of up to a month;
- A certified letter updating him/her on the study status.

Documentation of the contact attempts and the certified letter should be filed with the subject's source documents.

The reason for subject discontinuation or withdrawal from the study will be recorded in the eCRF. If the subject is discontinued from treatment due to an AE, the reason for discontinuation should be listed as due to an AE. The number of subjects screened may be adjusted to achieve the target number of subjects who receive at least 1 dose of study product.

Study product will be stopped without tapering because abrupt discontinuation of lenabasum is not known to cause any harmful effects. All remaining study product will be returned to the study staff.

## 6.2. Early Termination of Study

This study (either or both Part A and/or Part B) may be suspended or prematurely terminated at the discretion of the Sponsor if there is sufficient reasonable cause. For example, any new information about the execution of the trial, that, in the opinion of the Sponsor, contraindicates further study entry and randomization of new subjects, such as unsatisfactory enrollment with respect to quantity or quality, insufficient adherence to protocol requirements, data that are not sufficiently complete and/or evaluable, falsification of records, or determination of futility.

If any of the following events occur during enrollment, then study entry and randomization of new subjects into the study or rollover to Part B will be suspended until review of the event in question occurs by the DMC:

- Death in any subject considered to be related to lenabasum
- Two life-threatening clinical events judged to be probably- or definitely-related to lenabasum. NOTE: The term 'life-threatening' refers to an event in which the subject was at risk of death at the time of the event. It does not refer to an event, which hypothetically might have caused death, if it were more severe
- Determination of unexpected, significant, or unacceptable risk to subjects that contradict dosing of additional subjects, in the opinion of the Corbus Chief Medical Officer

Administration of study product may continue during the time of review in subjects who are already receiving study product in either Part A and/or Part B, based on the judgment of the Corbus Chief Medical Officer.

An expedited and cumulative review of safety data and the circumstances of the event(s) in question will be conducted by the DMC, with additional external expertise as needed, to make recommendations to the Sponsor whether study entry/randomization and dosing can resume or should be discontinued, whether the protocol should be modified, or whether the study should be discontinued permanently. Upon consideration of a cumulative review of safety and other data, the study may be discontinued permanently by the Sponsor.

Written notification, documenting the reason for study suspension or termination, will be provided by the Sponsor to the site investigators and relevant regulatory agencies. If the study is suspended or prematurely terminated, the site investigators will promptly inform their site IRB/EC and will provide the reason(s) for the suspension or termination. Review and approval by the reviewing IRB/IEC at each site may be required for resumption of the study in the event the study is interrupted.

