#### **4.5. Strategies for Recruitment and Retention**

The target enrollment (i.e., randomized and dosed) for this study is approximately 150 subjects. Most subjects will be recruited from clinics run by the investigators or at which the investigators participate. It is preferred that enrolled subjects have been followed in the investigator's clinic prior to study start. Advertisement for subjects outside the investigator's site is not preferred, although it is allowed.

Target screening of approximately 200 subjects (to achieve about 150 subjects randomized and dosed) is expected to take place over approximately 24 months and may be extended depending on enrollment rate. Number of subjects screened may be adjusted depending upon the screen failure rate, to ensure approximately 150 dosed subjects (mITT population). The number of subjects dosed may be adjusted depending on blinded interim analysis as noted in [Section 9.4.9](#).

To encourage retention in the study, every effort will be made to be respectful of the subject's time. The total time required from the subject for study visits will vary with the efficiency of each site and is expected to be about 4-5 hours for Visit 1, 0.5-1 hour for visits when efficacy assessments are not done, and 1-2 hours for visits when efficacy assessments are done.

Subjects will be encouraged to stay in the study at each visit by study personnel and reminded of the date and time of their next visit. If the subject agrees, e-mail or text message reminders of visits may be sent.

To reduce missing data, subjects who discontinue study product for reasons of safety or tolerability will be asked to remain in the study and return for evaluations on Visit 4, Visit 6, Visit 8 (if they have not already had Visit 4, 6, and 8) and Visit 10 unless the subject withdraws consent or is lost to follow-up. These off-treatment safety and efficacy data will be included in data analyses.

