#### **10.1.7.2. Data Monitoring Committee (DMC)**

Oversight of subject safety in this trial will be provided by an independent unblinded DMC, which will advise Corbus and the investigators. The voting members of the DMC will include at least 3 external experts in DM who will be supported by an un-blinded biostatistician, who will be a non-voting member. A non-voting member may be added to provide clarifications and historical perspective, at least during Open Sessions of the DMC meeting. Additional experts in areas related to DM, safety, or regulatory requirements or practices can be added as needed.

The independent DMC will review the accumulated safety and operational data about every 6 months through the last subject/last visit or more frequently, if necessary. The DMC will review interim/cumulative data for evidence of study-related AEs and factors external to the study such as scientific or therapeutic developments that may impact subject safety. The DMC will also review progress of the study and efficacy outcomes. The DMC may make recommendations to Corbus about any of the items it reviews. In addition, if any of the following events occur during the enrollment, then the DMC will review all cumulative safety information and the event(s) of interest:

- Death in any subject related to lenabasum.
- Two life-threatening clinical events that are probably or definitely-related to lenabasum.
- Determination of unexpected, significant, or unacceptable risk to subjects in the opinion of the Corbus Chief Medical Officer.

The DMC should conclude each review with written recommendations to Corbus as to whether the study should continue without change, be modified, or terminated. Recommendations regarding modification of the design and conduct of the study could include whether study entry/randomization and dosing should be discontinued, whether the protocol should be modified, whether the study should be discontinued permanently, and reasons for these recommendations.

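### The mandatory pause of Part B rollover and the event-driven DMC review end with enrollment, about 12 months before the last subject can roll over (minor; cheap to fix)

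*Protocol*

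**What the plan says.** Section 6.2 lists three triggers: a death attributed to lenabasum, two life-threatening events judged probably or definitely related to it, and a finding of unacceptable risk by the sponsor's Chief Medical Officer. If any such "events occur during enrollment, then study entry and randomization of new subjects into the study or rollover to Part B will be suspended" pending DMC review. The section adds: "An expedited and cumulative review of safety data and the circumstances of the event(s) in question will be conducted by the DMC".

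Section 10.1.7.2 repeats the triggers with the same time limit: "if any of the following events occur during the enrollment, then the DMC will review all cumulative safety information". Apart from that, the DMC reviews safety and operational data "about every 6 months through the last subject/last visit or more frequently, if necessary".

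Section 4.5 shows what enrollment means: "The target enrollment (i.e., randomized and dosed) for this study is approximately 150 subjects". Screening to reach that number is "expected to take place over approximately 24 months and may be extended depending on enrollment rate". Under section 3.1.2, subjects roll over on completing Visit 10 (Week 52), and everyone in Part B takes lenabasum 20 mg BID.

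Two further statements in section 6.2 bear on the point. Either part of the study "may be suspended or prematurely terminated at the discretion of the Sponsor if there is sufficient reasonable cause". And when a trigger fires, "Administration of study product may continue during the time of review in subjects who are already receiving study product".

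**The concern.** Section 6.2 names rollover as one of the activities to be paused, yet the rule stops operating when enrollment closes. Rollover cannot finish until a year after that. For its last stretch, an activity that the rule was written to control is outside the rule.

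For most subjects rollover is new exposure. Placebo subjects take lenabasum for the first time, and 5 mg subjects take four times their previous dose. Together they are 3/5 of those randomized under 2:1:2. Part A gives the first dose in clinic, with vital signs and an ECG about 3 hours later. Visit B1 lists only consent, reuse of the Visit 10 data and dispensing, and the next visit is at Week 4. Part A stays blinded until database lock (section 5.3), so the investigator who agrees to a rollover will generally not know who is new to the drug. An event-triggered review by the unblinded DMC would be the natural check at that point.

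Little is lost for the third trigger, which rests on the Chief Medical Officer's own judgement. The gap matters for the two event-based triggers.

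**Working it through.** **Inputs**
- Recruitment about 24 months (section 4.5)
- Part A treatment up to 52 weeks, rollover at Visit 10 (sections 3.1.1 and 3.1.2)
- Part A about 36 months from first visit to last visit (synopsis)
- 150 dosed, 120 expected to complete at least Week 28 (section 9.2)
- Allocation 2:1:2
- DMC review about every 6 months (section 10.1.7.2)
- Possible increase to 230 randomized and 183 completers (section 9.4.9)

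**1. The plan's own timeline.** 52 weeks × 12/52.1775 = 11.96 months, and 24 + 11.96 = 35.96 months, which reproduces the stated 36. Adding 4 weeks of screening gives 36.9, and adding 4 weeks of follow-up as well gives 37.8. All are compatible with the stated figure.

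**2. The uncovered period.** Enrollment runs from month 0 to about 24. Rollover runs from about month 12 to about 36. The part after closure is 36 − 24 = 12 months. This does not depend on how long accrual takes, because the last subject randomized always needs 52 weeks to reach Visit 10. For example, at the planned rate of 150/24 = 6.25 per month, 230 subjects take 230/6.25 = 36.8 months; rollover then ends at about month 48.8, still 12 months after closure.

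**3. How many subjects a missing pause could affect.** The pause lasts only until the DMC has reviewed the event. The relevant count is therefore those who roll over between an event and the next scheduled review, given that a trigger occurs and neither the sponsor nor the DMC acts sooner. Assume 120 completers, uniform accrual over 24 months, all completers rolling over, and equal dropout and uptake across arms.
- Rollovers per month: 120/24 = 5
- Event just after a review: 5 × 6 = 30
- Event at a random time in the interval, mean wait 3 months: 5 × 3 = 15
- Of these, from placebo or 5 mg: 30 × 3/5 = 18 and 15 × 3/5 = 9
- At 50% uptake: 15 and 7.5, of whom 9 and 4.5 from placebo or 5 mg

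**4. Sensitivity of the full-interval count of 30.**
- Accrual falling linearly, first 6 months after closure: [(12/24)² − (6/24)²] × 120 = 22.5
- Accrual rising linearly, last 6 months of rollover: [1 − (18/24)²] × 120 = 52.5
- 183 completers accrued in 24 months: 183/24 × 6 = 45.8
- 183 completers at the planned rate: 183/36.8 × 6 = 29.8

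All counts fall if fewer subjects reach Week 52 than Week 28, since section 9.2 ties the 120 to Week 28.

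**The case against.** The strongest reply has three parts.

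First, enrollment is nowhere defined as a period. Section 4.5 glosses a headcount, and a reader guided by purpose could take the word in section 6.2 to include entry into Part B, since the same sentence mentions rollover. The wording may simply be loose. But the protocol calls entry to Part B rollover, and section 6.2 lists it separately from study entry and randomization. A mandatory safety rule should not depend on a generous reading. It is also fair to say that the sentence is not self-contradictory: rollover and enrollment overlap from about month 12 to 24, so naming rollover there makes sense.

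Second, oversight does not stop when enrollment closes. The unblinded DMC continues through the last visit and may meet more often, and section 5.3.2 requires its final safety review before the Part A lock. The sponsor may suspend either part. Serious events are reported within 24 hours, the individual stopping rules of section 6.1 apply, and each rollover needs consent and the investigator's agreement. A reader might infer that late rollovers are unprotected; the document does not support that. What stands is narrower: none of these provisions obliges a pause in rollover or an expedited DMC review.

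Third, a reader might count every rollover after closure, 120 × 12/24 = 60, as the size of the problem. That overstates it, because the pause would last only until the DMC had looked at the event.

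**Conclusion.** The point holds as a minor gap in the wording of a safety rule. For about 12 months after the last randomization, the two event-based triggers neither pause rollover nor require an expedited DMC review, although section 6.2 names rollover as something to pause.

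If a trigger event occurred then and nobody acted before the next scheduled review, at most about 30 subjects would roll over in the meantime and about 15 on average, roughly 18 and 9 of them from placebo or 5 mg. This rests on 120 completers, uniform accrual over 24 months, full uptake and reviews 6 months apart. The figures count exposure, not harm, and the protocol gives no basis for the probability of a trigger event.

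A reader might go further and want event-driven DMC review made mandatory through the whole open-label extension. The rollover argument does not carry that far. Section 6.2 lets ongoing dosing continue during a review even when a trigger fires, and section 3.1.2 allows the extension to run beyond a year with no stated end, so such a rule could keep the DMC in place indefinitely.

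**What to change.** In section 6.2, replace *during enrollment*, and in section 10.1.7.2 replace *during the enrollment*, with: *while any subject may still be randomized or roll over to Part B*. The expedited review in section 6.2 then has the same scope. Leave the triggers and the Chief Medical Officer's discretion over ongoing dosing as they are.

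The edit is one phrase in each section. If an event occurs after enrollment closes, it may cost one extra DMC meeting and a temporary treatment gap for subjects who reach Visit 10 during the pause, including 20 mg subjects who already tolerate that dose. The present rule already accepts such a gap during enrollment, and section 6.1 says that stopping lenabasum abruptly has no known harmful effect. What remains is possible loss of benefit during the gap.

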## **7. SCHEDULE OF ASSESSMENTS AND STUDY VISITS**

### **7.1. Assessments**

**Table 3 Schedule of Assessments – Part A**

Study Activity	Visit	Screening	Treatment Period										ET	Follow-up x 4±1
			V1	V2	V3	V4	V5	V6	V7	V8	V9	V10		
	Week	Up to -4	Day 1	4±1	10±1	16±1	22±1	28±1	34±1	40±1	46±1	52±1		
ELIGIBILITY ASSESSMENTS														
Informed Consent		X											X w	
Eligibility criteria	X		X											
Medical history	X													
Physician assessment of DM activity	X													
Concomitant medications	X	X	X	X	X	X	X	X	X	X	X	X	X	X
Vital signs and weight	X	X	X	X	X	X	X	X	X	X	X	X	X	X
Height	X													
Full physical examination	X	X											X	X
Brief physical examination			X	X	X	X	X	X	X	X	X			X
HIV, HBV and HCV testing	X													
FSH and LH	X													
Contraceptive assessment and record LMP for WOCBP	X	X	X	X	X	X	X	X	X	X	X	X	X	X
Serum β HCG for WOCBP	X													
Urine β HCG for WOCBP			X	X	X	X	X	X	X	X	X	X	X	X
SAFETY ASSESSMENTS														
AE monitoring	X	X	X	X	X	X	X	X	X	X	X	X	X	X
12 lead ECG	X	X	X					X				X		X
Safety phone call to subject												X		
RANDOMIZATION														
Randomization (IWRS)			X											
STUDY PRODUCT ADMINISTRATION														
Administer study product in clinic			X											
Dispense study product			X	X	X	X	X	X	X	X	X			
Collect and count capsules of returned study product				X	X	X	X	X	X	X	X	X		X
PATIENT-REPORTED EFFICACY ASSESSMENTS														
PtGA	X	X	X		X		X		X		X		X	X
HAQ-DI	X	X	X		X		X		X		X		X	X
SF-36	X	X	X		X		X		X		X		X	X
PROMIS-29 Short Form	X	X	X		X		X		X		X		X	X
Patient VAS score for pain	X	X	X		X		X		X		X		X	X
FACIT-Fatigue Score	X	X	X		X		X		X		X		X	X

Study Activity	Visit	Screening	Treatment Period										ET	Follow-up a 4±1
			V1	V2	V3	V4	V5	V6	V7	V8	V9	V10		
	Week	Up to -4	Day 1	4±1	10±1	16±1	22±1	28±1	34±1	40±1	46±1	52±1		
5-D Itch Questionnaire		X	X	X		X		X		X		X	X	
Skindex-29+3		X	X	X		X		X		X		X	X	
EQ-5D questionnaire		X	X	X		X		X		X		X	X	
PHYSICIAN ASSESSMENTS OF EFFICACY														
MMT-8		X	X	X		X		X		X		X	X	
CDASI score		X	X	X		X		X		X		X	X	
IGA scale of skin activity		X	X	X		X		X		X		X	X	
EMGA (10 cm VAS)		X	X	X		X		X		X		X	X	
MDGA (10-cm VAS and Likert Scale)		X	X	X		X		X		X		X	X	
LABORATORY ASSESSMENTS														
CBC with differential and platelets		X	X	X	X	X	X	X	X	X	X	X	X	
Metabolic panel (includes ALT, AST and LDH)		X	X	X	X	X	X	X	X	X	X	X	X	
CK and aldolase		X	X	X		X		X		X		X	X	
Blood biomarkers			X					X				X	X	
Blood for flow cytometry (at selected sites)			X					X				X	X	
Paxgene tube collection			X									X	X	
Autoantibody measurements			X									X	X	
Urine dipstick			X	X				X				X	X	
PHARMACOKINETIC ASSESSMENTS														
Lenabasum plasma concentration and metabolite profiling			X	X		X		X				X	X	
ADDITIONAL ASSESSMENTS														
Spirometry		X	X			X		X				X	X	
Skin biopsies (optional at selected sites)			X			X						X	X	
Skin photography (optional at selected sites)			X									X	X	
Patient Improvement Questionnaire for Subjects						X		X				X	X	
Patient Improvement Questionnaire for Physicians						X		X				X	X	

a Must fulfill Bohan and Peter's criteria for probable or definite DM or ACR/EULAR criteria for DM

b Medical history includes the following: subject demographic information, history and disease manifestations of DM including ILD, concurrent illnesses and past, smoking history (packyears) classified into one of the following categories: current smoker; ever smoked (>= 1 cigarette/day for > 1 year); never smoked, and any other relevant medical history.

c Doses of immunosuppressive medications (including corticosteroids) should be assessed at every study visit along with all other concomitant medications.

d Systolic and diastolic BP will be measured with the subject supine for at least 5 minutes. The same arm should be used for the measurement throughout the study as much as possible. Pulse and respiration will also be measured with the subject supine for at least 5 minutes. Body temperature will be measured on the skin or in the mouth.

e Weight will be measured with coats, jacket, and footwear removed.

f Standing height will be measured with footwear removed.

g Full physical examination includes the following assessments: alertness and orientation, general appearance, skin, head, eyes, ears, nose, and throat, lungs, heart, abdomen, musculoskeletal examination, and lymph nodes. Breast and genitourinary examinations are not required.

h Brief physical examination includes the following assessments: skin, lung, heart, abdomen, and any other area as indicated by changes in medical history.

i Applicable for women  $\leq$  55 years of age with no menses for  $\geq$  1 year.

j Refer to [Appendix 1](#) for the criteria for determining reproductive potential and acceptable methods of contraception.

k AE monitoring should begin at subject consent.

l 12-lead ECG with QT/QTc intervals should be recorded with the subject in a rested supine position  $\geq$  10 minutes before the test.

m Study personnel will be required to contact subjects  $3 \pm 1$  week after Visit 9.

n To occur at or before Visit 1.

o The first dose of study product on Visit 1 will be taken in clinic from the dispensed study product. Vital signs include blood pressure, pulse rate, respiratory rate, and temperature and will be measured pre-dose and  $3.0 \pm 0.5$  hours after administration of first dose of study product at Visit 1 in the clinic. ECGs will be recorded pre-dose and  $3.0 \pm 0.5$  hours after administration of first dose of study product in the clinic.

p Study product will be dispensed for administration in WOCBP only if urine pregnancy test is negative.

q Ideally, all patient-reported efficacy assessments should be completed before all other study procedures, in the order listed.

r It is preferred that physician assessments of efficacy are performed in the order listed.

s Metabolic panel includes glucose, urea nitrogen, creatinine, estimated glomerular filtration rate, blood urea nitrogen/creatinine, sodium, potassium, chloride, carbon dioxide, calcium, protein total, albumin, bilirubin total, alkaline phosphatase, aspartate aminotransferase (AST), alanine aminotransferase (ALT), lactate dehydrogenase (LDH); AST, ALT and LDH are three of the five muscle enzymes comprising the TIS (see [Section 8.1.2](#)).

t Urine dipstick for blood, protein, glucose

u Pharmacokinetic blood samples will be collected at Visit 1 pre-dose and  $3.0 \pm 0.5$  hours after administration of first dose of study product in the clinic. Time of administration of the first study dose and time of PK sample collection (blood draw for PK) should be recorded. At Visits 2, 4, 6, and 10, PK blood samples will be collected once during the visit and time of most recent dose of study product and blood collection should be recorded. Time of the blood draw should be 8-16 hours after the last dose of the study product, which typically would have been taken at subject's home the evening before the visit.

v Five optional, 4 mm skin biopsies will be collected: two at Visit 1, two at Visit 4 and one at Visit 10. At Site 1001, subjects will have the option to consent to two 6 mm and three 4 mm biopsies (e.g., one 4 mm and one 6 mm at Visit 1; one 4 mm and one 6 mm at Visit 4, and one 4 mm at Visit 10). Skin biopsies will only be conducted at selected sites.

w Subjects who rollover into Part B should sign an ICF by Visit 10 and preferably earlier than Visit 10, if possible.

x The Safety Follow-up Visit is to occur  $4 \pm 1$  weeks after the last visit (V10/ET) and is to be completed by subjects who do not rollover into Part B.

